Objectives	
The primary objectives of the SHAReD study are:
 
 1. Does the implementation of an online shared care plan (the intervention) improve the frequency and quality of primary and preventive care received by study participants in intervention sites compared to participants in sites with usual care 3 months after their reported usual shared care ? 
The secondary objectives are:
 
 2. Does the intervention better integrate care between mental health services and general practice compared with usual care 3 months after their reported usual shared care ? 3. Does the intervention improve consumer health risks and service use compared with usual care 3 months after their reported usual shared care? 4. What are the main costs and health outcomes associated with the intervention and usual care situations, is the intervention more cost-effective compared to usual care, and are there any costs avoided (saved) 3 months after their reported usual shared care?
Study design	Pragmatic trial with the unit of randomisation being four of the five Adult Community Mental Health 'Core' Teams in Sydney Local Health District (SLHD). Pairs of teams (matched by service type and consumer population) randomised to early or late intervention 3 months after their reported usual shared care.
Planned sample size	500 consumers and their shared-care GPs
Selection criteria	
Inclusion criteria are:
 
 1. People who are clients of the SLHD Adult Community Mental Health 'Core' Teams in Canterbury, Croydon, Camperdown and Marrickville and the GPs that these consumers nominate. 2. Age: 18+ years 3. Engaged in shared care or willing to commence a shared care arrangement before participating in a baseline survey. 4. Intervention group: Has a GP engaged in shared care who consents to participate in the study and to have the electronic care plan installed. 5. Willing to provide informed consent and willingness to participate and comply with the study requirements. 
Exclusion criteria

	
Unable to give informed consent.
 
Unable to speak English or a language not supported by the study.

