
Study Procedure
	
 1.SLHD Adult Community Mental Health 'Core' Teams will be randomised to – 1 of Canterbury or Croydon and 1 of Camperdown or Marrickville will be randomly allocated to the intervention group and the other will receive delayed intervention 2.500 People with severe mental illness (PWSMI) who have contact with these teams and who are identified as suitable by the Core team staff member who is their care coordinator during routine visits will be given written information about the study. With the consumer’s permission, care coordinators will provide the research team with contact details of consumers who are interested in participating in the study. 3.A research officer will contact these potential participants to explain the study, answer any questions, and obtain informed consent. 4.Participant consumers will be asked to approach their GP to be part of the project OR consent to the research team doing so on their behalf to recruit GPs to the study. 5.If GPs provide consent to participate in the study, they and their patient are enrolled in the study and an appointment is made to install the INCA shared care software in the GP practice’s computer and arrangements will be made to train the GP in its use and a baseline survey is conducted with the consumers and their shared-care GPs. 6.Consumers in the intervention group will have their physical health care coordinated through an online shared care plan. 7.Consumers in the comparison group will receive usual care. 8.If GPs withdrew consent to participate in the study, their patient will remain enrolled in the study and will be able to participate in a repeat interview 3 months after their reported usual shared care. 9.Consumer and GP participants will participate in a repeat interview 3 months after their reported usual shared care. If any consumer does not have a shared care appointment/follow-up since baseline, they will be invited to participate in the repeated interview three months after 30 June 2023 (i.e., 3 months after the deadline for the intervention to be implemented). 10.With consent and approval, relevant health service use and clinical data will be extracted from medical records held by GPs, datasets held by SLHD, HealthNet (including MBS/PBS items), and the NSW Ministry of Health (ICOD). 11.A subset of consumers will be invited to participate in a qualitative interview after 3 months of their reported usual shared care. 12.A subset of SLHD mental health clinicians (Care Coordinators and shared care clinicians) and GPs will be interviewed after the intervention period.

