4.4. ENDPOINTS

PRIMARY ENDPOINTS

Differences between the intervention and comparison groups in changes in the frequency and quality of preventive care from their reported usual shared care to 3-months:

1. Increased % of consumers for whom each health risk is measured and recorded over the preceding 3 months*
2. Increased % consumers who have been vaccinated against influenza over the preceding 3 months
3. Decreased % consumers with high CVD risk who have not received a prescription for either an anti-hypertensive or lipid lowering drug.
4. Increased % consumers who report advice/referral for smoking cessation, diet education and physical activity over the preceding 3 months.

* Health risks are itemised in Table 3.

SECONDARY ENDPOINTS

Differences between the intervention and comparison groups in changes from their reported usual shared care to 3-months:

5. Increased % MHS consumers have a care plan (GPMP and TCA) in last 3 months
6. Increased consumer rating of extent to which providers (MH & GP) are working to a common care plan in the past 3 months
7. Improved quality of communication between MHSs and GPs in last 3 months
8. Reduced number of ED attendances and hospitalisations in last 3 months
9. Increased number of visits to GP in last 3 months
10. Improved consumer experience of providers (MH & GP) working to a common (shared) care plan in the past 3 months (qualitative analysis)
11. Increased scores on Domain 1 (Feeling understood and supported by healthcare providers) and Domain 7 (Navigating the healthcare system) of the Health Literacy Questionnaire
12. Increased score on Patient Activation Measure (PAM-13)
13. Improved diet and physical activity behaviours
14. Reduced Absolute Cardiovascular Disease Risk score **
15. Reduced diabetes risk score using AUSDRISK ***
16. Improved levels of most recently recorded results from health risk screening*
17. Reduced costs of hospitalisations in last 3 months
18. Reduced out of pocket costs of participants
19. Improvements in Quality of Life as assessed by the EQ5D-5L.

* Health risks are itemised in Table 3.

** Information needed for CVD risk score is provided in Table 4

*** Information needed for AUSDRISK score is provided in Table 5.

Table 3 Health risks

Health risks	Units/options	Normal range/goals
Systolic & diastolic blood pressure (BP)	mmHg	<130/85 mm Hg

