- The capacity of the consumer to consent to the research will be assessed his/her mental health care coordinator, who is qualified to judge the capacity of their patients. Where there are any concerns, this will be discussed with the consumer's treating psychiatrist.
- Care coordinators will advise the research team of any changes in the participant's capacity to consent and to participate in the research.
- Care has been taken in the design of the interviews and will be taken in the training of interview staff to ensure that the interview does not increase consumer's discomfort or distress and to ensure that, if this were to occur, that the interview would be stopped and the consumer supported and referred appropriately.

RECRUITMENT OF GPs

1. After a consumer has consented to participate in the study (which includes consent to the research team contacting their GP about study participation), the research team will contact the consumer's GP. The name of the GP and their practice will be confirmed with the consumer.
2. If feasible, a letter from the consumer is posted to the GP informing that the consumer has consented to be in the study and inviting the GP to be in the study (Appendix 15.2). The letter states: *"The research team will contact you shortly or you can contact the Research Manager, [name]"*.
3. The GP contact details are recorded by the MH clinician in an Excel database on the SLHD MS Teams folder and shared with the research team.
 - 3.1 Intervention group: Details of GPs who decline will not be retained after data collection has completed. They will be retained during the data collection period because consumers are known to change GPs and this information is likely to be necessary to follow up.
 - 3.2 Comparison group: Details of GPs who decline but whose consumers consent to participate, will be retained. They will be retained because consumers will receive their usual shared care (no need for the GP to install the electronic care plan), and this information is likely to be necessary to follow up.
4. The research team will use a script when they contact the GPs (Appendix 15.4).

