5.4 CONFOUNDERS

Any baseline differences between clients seen by intervention and comparison teams in demographic or socioeconomic characteristics and mental health condition may act as potential confounders. These will be assessed in the analysis and, if necessary, adjustment made in analyses.

Another potential confounding factor could be that patients will accumulate around the GPs with the most engagement in the study who have the shared eMR (electronic medical record) installed early on. MHS case coordinators will be asked to monitor whether any consumers have changed GPs as a result of the trial and inform the study investigators if this happens. We cannot stop consumers from changing GPs, but we can only monitor if this happens. Our experience with this consumer group is that changing GPs is unlikely unless a consumer is dissatisfied with their existing GP.

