	GP visits 6-month period post-intervention* (May-October 2023) compared with the 6-month periods: 
 • Pre-intervention (November 2022-April 2023) • In the previous year (May-October 2022, to check for seasonal effect) 
*"intervention" = shard care plan in Inca (May-June 2023)
	GP records EMR Report (CMH011 Document Audit)
	Number of consumers engaged in Mental Health Shared Care arrangements and applicable outcomes, GP contact details	EMR Reports (AMH Current Clients; AMH Metabolic Monitoring) (Appendix 14),
	Consumer experience of providers (MH & GP) working to a common care plan in last 2 years	Consumer and carer qualitative interviews
4 consumer health risks	Consumer health literacy score in last 6 months	Consumer survey
	Consumer health risk behaviours in las 6 months	
	Consumer diabetes risk score on AUSDRISK in last 6 months***	

Concept	Secondary Outcomes	Data source
5 Cost-consequence and cost-effectiveness	Costs of hospitalisations and other healthcare services avoided 6-month period post-intervention* (May-October 2023) compared with the 6-month periods: 
 • Pre-intervention (November 2022-April 2023) • In the previous year (May-October 2022, to check for seasonal effect) 
*"intervention" = shard care plan in Inca (May-June 2023)
	Hospitalisations data, SLHD Healthcare Use (especially hospitalisations, length of stay, procedures) and Cost data using medical record numbers, Consumer survey, eMR Reports 'AMH Current Clients', 'CMH011 Document Audit', and 'AMH Metabolic Monitoring', SLHD Targeted Activity & Reporting System (STARS)
	Consumer quality of life score on EQ5D-5L in last 6 months	Consumer survey

* See Table 3

** See Table 4

*** See Table 5

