9. DATA COLLECTION

9.1 Overview of forms for each data collection

Types of data and their respective forms (if applicable) are listed below, followed by a description of the procedures for data collection.

1. Existing (secondary) consumer data:
 - a. general practice records extracted via PenCat and Polar
 - b. SLHD Data from the Integrated Care Outcomes Database (ICOD) (Specific items in Appendix 1)
 - c. ED Presentations, hospitalisations and medical treatment data using medical record numbers from the SLHD Performance Unit (Appendix 14)
 - d. [EMR Reports \(Area Mental Health \(AMH\) Current Clients; CMH011 Document Audit; AMH Metabolic Monitoring\)](#) (Appendix 14)
 - e. [STARS Report \(Community Ambulatory MH Report\)](#) (Appendix 14)
2. Quantitative data from:
 - a. Consumer questionnaire (Appendix 3)
 - b. Provider questionnaire (Appendix 4)
3. Qualitative data via interviews with:

- a. Consumers and carers (Appendix 6)
- b. Providers. (Appendix 7).

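### GP visits are taken from practice records with no clear count of visits at other practices, so a change in where consumers go can look like a change in how often they go

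*Protocol*

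**What the plan says.** **The outcome.** Section 4.4 lists secondary endpoint 9 as "Increased number of visits to GP in last 3 months". Table 9 in section 7 sets it up as "GP visits 6-month period post-intervention* (May-October 2023) compared with the 6-month periods" before the intervention and one year earlier. (The 3-month and 6-month windows disagree. That is a separate inconsistency and is not pursued here.)

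**The source.** The Table 9 entry for this row is "GP records EMR Report (CMH011 Document Audit". Section 9.1 describes the first part as "general practice records extracted via PenCat and Polar". The GPs in the study are, in the synopsis selection criteria, "the GPs that these consumers nominate". Section 5.3 describes them as the consumer's shared-care GP and lists giving access for a data extract as one of the reimbursed components of GP participation.

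**What the protocol says about GP use.**
- Section 5.3, recruitment of GPs: in the intervention group, details of GPs who decline are kept during data collection because "consumers are known to change GPs and this information is likely to be necessary to follow up".
- Version control box, version 7: the consumer survey gained questions on choice and pattern of GP use and was reworded to allow for more than one GP.
- Section 5.4: a potential confounder could be that "patients will accumulate around the GPs with the most engagement in the study". The response is monitoring by mental health staff. The same paragraph says a change of GP is unlikely unless the consumer is dissatisfied.

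**A second source, used elsewhere.** The synopsis (Study Procedure, item 10) and section 4.5 plan extraction from "HealthNet (including MBS/PBS items"). Table 9 adds HealtheNet to GP records for the prescribing outcome, but not for GP visits.

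**The concern.** A visit count answers the question in endpoint 9 only if the source sees the consumer's visits wherever they take place, or if the outcome is labelled as visits to one practice. Table 9 does neither. It names a practice-based source and gives no rule for visits at a second practice or for visits before or after a change of GP.

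The gap matters for the comparison because the share of visits captured may change after allocation. Under sections 1.1 and 6.2 the online plan sends reminders, and its tasks are completed at visits to the GP on the plan. If that draws visits from other practices to the study practice more strongly than usual shared care does, the same total appears as a higher count, and a higher count is what the endpoint looks for. Randomisation does not protect against this, because the shift follows allocation. Comparison with the two earlier windows does not remove it either, because the capture share itself may differ between windows.

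**Working it through.** The protocol gives no visit rate, standard deviation, effect size or share of visits made elsewhere, so it has no figure to reproduce. The shares below are assumptions. They show how the bias behaves and do not estimate it.

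**1. Set-up.** Let *s* be the share of a group's GP visits that the source captures. Then recorded visits = *s* × true visits.

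**2. Equal and stable capture.** If both arms have the same *s* throughout, the recorded ratio is (*s* × true visits, intervention) / (*s* × true visits, comparison), and *s* cancels. The level is too low, and an absolute difference shrinks by the factor *s*, but no spurious effect appears.

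**3. Capture changes in the intervention arm, true visits unchanged, comparison arm stays at *s0*.** Apparent ratio = *s1* / *s0*.

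| Captured before (*s0*) | Captured after (*s1*) | Apparent ratio |
|---|---|---|
| 60% | 90% | 0.90/0.60 = 1.50 |
| 70% | 80% | 0.80/0.70 = 1.14 |
| 70% | 90% | 0.90/0.70 = 1.29 |
| 80% | 90% | 0.90/0.80 = 1.13 |
| 90% | 100% | 1.00/0.90 = 1.11 |

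**4. Whole consumers join the captured practice** for the post period only, with their earlier visits unseen. For a proportion *m*, apparent ratio = 1/(1 − *m*): 5% gives 1.05, 10% gives 1.11, 20% gives 1.25.

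**5. Consumers leave the captured practice halfway through the window.** They lose half of their recorded visits, so apparent ratio = 1 − *m*/2: 5% gives 0.975, 10% gives 0.95, 20% gives 0.90.

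**6. Reading.** Steps 3 and 4 push the result towards the hypothesised increase and step 5 pushes it away. The direction depends on which movement dominates and by how much the arms differ. The documents settle neither.

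**The case against.** The strongest reply has five parts.

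- **The text does not limit GP records to the nominated practice.** This is correct. Contact details are kept partly because consumers move, so a new GP's records might be sought, and the protocol does not describe what the CMH011 report shows about visits elsewhere. A reader might infer that outside visits cannot be seen at all. The documents support only that they are not clearly counted. Even so, extraction depends on a practice giving access, so the study GP's practice remains the natural reading.
- **Movement may be rare.** A reader might take section 5.4 to expect accumulation around engaged GPs. It names this only as a possibility, and calls GP change unlikely. That sits uneasily with section 5.3, and it does not address consumers who see several GPs at the same time.
- **Both arms have a shared-care GP.** A reader might infer that visits concentrate in the intervention arm only. The documents do not support that, since section 1.1 frames the comparison as online against paper plans with the same content. Some concentration can occur in both arms, and only a difference between arms biases the ratio (step 2). Reminders may also prompt truly additional visits, which is the intended effect.
- **The alternative source is unproven.** A reader might infer that the MBS items cover all practices. No section says so, and the MBS/PBS appendix is listed but not shown. Coverage has to be confirmed before they are relied on.
- **GP costs need not be affected.** Section 8.2 lists GP care among the usage data, but it assigns GP records to research questions 1 and 2, and the cost row of Table 9 does not list them. An error in GP costs is therefore not established.

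Detailed counting rules may well sit in a statistical analysis plan that is not at hand, and visits to the shared-care practice would be a defensible outcome if it were labelled so. What stands is that the protocol itself names the source, the source probably under-captures the outcome as worded, and the protocol supplements the same kind of record for prescribing.

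**Conclusion.** The point holds as a problem of how the outcome is captured. As Table 9 stands, visits outside the study practice are not clearly counted, and any difference between arms in how far visits concentrate there would be read as a difference in the number of visits.

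The size cannot be derived from the protocol. Under assumed shares, with no true change in visits, capture rising from 80% to 90% in the intervention arm alone gives an apparent ratio of 1.13, and 10% of consumers leaving midway gives 0.95. A reader might conclude that the trial is biased in favour of the intervention. The documents support only that it could be biased in either direction. GP visits is one of fifteen secondary endpoints (items 5 to 19 in section 4.4), so the primary conclusion does not depend on it. The change is still worth making because it is cheap.

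**What to change.** 1. **Table 9, GP-visits row:** name the HealtheNet MBS items as the main source, in both arms and for all three 6-month windows. Before finalising, confirm that they cover all practices, all three windows and all consumers. Add HealtheNet to the secondary-data list in section 9.1, where it does not appear.
2. **Keep the practice-record count** as a separate measure, labelled as visits to the shared-care practice. State which practices are extracted and how a change of GP is treated.
3. **Where MBS items are unavailable,** report the outcome under that narrower label and run a sensitivity analysis using the survey items on pattern of GP use. Check that those items survive: the version 10 entry in the version control box records that survey questions were deleted, and the survey itself is not shown. Do not end a consumer's observed time at a change of GP. That would censor on an event after randomisation that may be related to engagement, and it would do nothing for consumers who see several GPs at once.
4. **If GP care is costed,** use the same source as for the visit count.

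The cost is a change to one table cell, one list entry and a few lines of analysis text, using an extraction that is already planned. The downside is that MBS linkage may be incomplete for some consumers.

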8. STATISTICAL CONSIDERATIONS

8.1. SAMPLE SIZE OR POWER CALCULATION

We aim to recruit 500 consumers and expect 400 to remain in the study at 9-month follow-up (20% loss to follow up). Power calculation: Assuming 20% change, a sample size of 91 per group is required to detect a change from 30 to 50% in primary outcomes based on $\alpha = 0.05$, $1-\beta = 0.8$. Assuming a design effect due to clustering of 2, a total sample of 360 is required (180 in each group).

8.2. PROVIDE A DETAILED ANALYSIS PLAN

Quantitative analysis

The fidelity and tailoring of the intervention to participants' needs will be assessed by analysing records, provider and consumer interviews 3 months after their usual shared care appointments. We will compare outcomes over 3 months after intervention between SHAReD intervention and comparison groups with linear or generalised multi-level mixed models including age, sex and key independent variables that are found to be significantly different between groups at baseline. Intra-class correlations will be calculated to compare the amount of variance associated with design features such as individual participants nested within care coordinators who are nested within community mental health teams, and those same participants are also nested within GPs who could also be nested within medical centres, before selecting random effects for these statistical models. As well as an analysis of completers (defined as those consumers, care coordinator and GP who

consented and are engaged in shared care), an intention to treat (ITT) analysis will also be included for this project. For the ITT analysis, those who drop out of the study (defined as consumers who were discharged of shared care or who withdrew consent) will be treated using a variety of sensitivity analyses including multiple imputation for the missing values on key measures resulting from them dropping out of the study. Sensitivity analyses will assess unmeasured variation.

Qualitative analyses

This will evaluate the experience of participants, carers and providers, barriers to implementation, conditions for sustainability and translation. Qualitative data will be managed and coded using NVivo 11 analysis software (QSR International). Two researchers will review each transcript and develop coding aligned with the Theoretical Domains Framework and Normalisation Process Theory.^{25,26} Coding will be predominantly deductive but inductive coding will also be applied to detect new and emerging themes.

Data combining and cost analyses

Secondary data from GP records, and SLHD eMR data (including hospitalisations, ED visits and ambulatory care records, associated costs, documentation audit report and metabolic report) as well as information from SLHD Targeted Activity & Reporting System (STARS) will be obtained and merged with the consumer survey data within the SLHD by AI [name]/AI [name]. GP records will be used to answer research questions 1 and 2 – quantitative analysis is described above. SLHD's patient data from the eMR (including hospitalisation, ED visits, ambulatory data, documentation audit and metabolic monitoring) as well as information from STARS and cost information will be used to answer research questions 3 and 4. These analyses of the resulting combined and de-identified dataset are described below.

The merged SLHD administrative data (micro-level data) will be from a 6-month period post-intervention (May-October 2023, considering the intervention as having a shared care plan in Inca between May and June 2023) compared with the 6-month periods, a) pre-intervention (November 2022-April 2023) and b) in the previous year (May-October 2022, to check for seasonal effect). The data will be analysed as part of the healthcare cost component (in the larger health economic evaluation).

The healthcare usage (such as hospitalisations, ED visits, ambulatory care and GP care) data will firstly be grouped in a meaningful way e.g., for hospitalisations, summarised by ARDRGs, diagnoses and average length of stay. Costs will be summarised too e.g., for hospitalisation costs, these will be described in terms of main components such as 'Medical', 'Nursing' and 'Allied Health' costs occurring during admissions. We will calculate the total and mean utilisation of healthcare services and costs (and undertake further econometric analyses) for those in the SHAReD intervention, usual care, and combined (SHAReD and comparison) groups. These summary statistics (and later modelled estimates) will be included in the cost component of the economic evaluation.

Additionally, it will be informative to measure the healthcare costs of SMI from the viewpoint of the SLHD/NSW health system, expressed as average total costs of SMI treatment per person under the alternative care situations. The SHAReD care group may be broken down into several subgroups for the analysis, and based on the degree to which they completed the intervention (e.g. their adherence to the shared e-plan, how many times they were engaged with the essential components

of the intervention and what they received, the quality of SHAReD care delivery, and participant acceptability and responsiveness to the intervention).²⁷ All costs will be expressed in 2023 Australian dollars.

Econometric methods commonly used to address issues associated with healthcare usage and cost variables such as problems of heteroscedasticity and skewness will be applied in this study.²⁸ These methods will be used to estimate the total (and differences in/incremental) costs (and costs specific to single and multiple health conditions, health risks, cardiometabolic outcomes) associated with the SHAReD care situation versus usual care adjusted for several participant and system-level characteristics. Various econometric methods will be explored such as log-transformed ordinary least squares models, GLMs (and may be those for repeated measures/panel data too) and survival (duration) models, with “goodness of fit” and other statistical measures used to make decisions about the models.²⁹

There may be missing data especially from the survey or general practice or as a result of merging data. This will be addressed by multiple imputation in the analysis.

To address confounding, variables with baseline differences between SHAReD intervention and usual care will be included in the final multivariate regression analysis.

To manage any risk that merging databases of non-identifiable data could subsequently result in the individuals being identified, data will be de-identified after combining the SLHD eMR data and costs with consumer survey data and stored securely (see section 12 of protocol). Only data with more than five individual responses will be released.

Costing component and the economic evaluation

An economic evaluation of the online shared care intervention (SHAReD) compared to usual care will be undertaken using the healthcare viewpoint. All relevant healthcare resources and health effects/benefits for the intervention and usual care groups will be identified, accurately counted and valued.

The healthcare resources used for delivering the SHAReD intervention and usual care will be identified, collected/estimated by researchers or clinicians delivering care, and valued. For the SHAReD intervention group, these will consist of the time of clinicians to develop the SHAReD care training program for staff, consumers and GPs; the materials used during the training (e.g. printing, travel time); the time of the facilitators to provide the staff training; and estimates of the time involved in general practice from encounter data and tasks (setting up care plan, making changes to or updating the care plan, communication with Mental Health team); essential infrastructure used; new technology purchased and used; training and supervision time for SHAReD participants and GPs; key medical treatments as per the description of the SHAReD intervention (such as medical tests, pathology, and medications); and consumables. The eMR reports such as CMH011 Document Audit, AMH Current Clients and AMH Metabolic Monitoring may be accessed by AI [name] and AI [name] to identify any relevant healthcare items and costs. For both groups, the occurrence of hospital admissions, Emergency Department visits and other health service usage (such as ambulatory care) will be measured and valued. These data will be sought from the SLHD's

patient data collection using medical record numbers (and eMR) and associated SLHD costings during the study. Costs attributable to the research will not be considered. Estimates of how the work of clinicians (and thus costs) has changed from the situation without the SHAReD intervention will also be explored during the focus groups. Variations in healthcare usage (such as hospitalisations and other medical treatment sought) and costs occurring later in the study (and up to 3 months post completion of the intervention) will be sought from SLHD eMR reports and the SLHD Performance Unit for cost of ED presentations and hospitalisations. The mean costs in the SHAReD intervention and usual care groups will be compared in addition to the mean health effects/benefits such as the care plan completion rate, quality of care received, clinical metrics, hospital admissions (and readmissions), hospital length of stay, and score on the utility-based and disease-generic quality of life measure (EQ5D-5L).^{30,31}

Having data on both the healthcare resource utilisation (costs) and health effects/benefits for the different groups will allow us to undertake a detailed cost-consequence analysis (CCA) – a first step for the economic assessment. CCA is a widely used form of economic assessment and recommended for reporting on health interventions with significant complexity and when there are multiple effectiveness measures such as programs/models of care seeking to address a range of clinical outcomes (Drummond et al 2005), and broad-reaching programs that have a range of health and non-health related effects needing to be quantified and assessed (NICE 2017). For this initial step of the economics work, the relevant costs and multiple outcomes will be calculated and presented in a disaggregated way which enables decision-makers to assess the relative importance of each component to the context they face. The comparator will consist of those consumers who did not receive the SHAReD intervention. Descriptive analysis will be used to estimate the total and mean costs (and standard deviations) associated with the intervention and usual care, as well as the effectiveness information (outcomes) and reported in a disaggregated manner.

A within-trial economic evaluation of the SHAReD intervention compared to usual care will be conducted if effectiveness has been demonstrated. The mean costs and health effects/benefits will be used to generate the incremental cost for a one-unit improvement in the health effect of interest (e.g. an extra Quality Adjusted Life Year [QALY]) for the SHAReD group compared to the usual care group. We will assemble several ICERs such as the incremental cost for each care plan completed, the reduction in cases with cardiometabolic risk (and separate risk factors), unplanned hospital admissions avoided, and a gain in QALYs among the SHAReD group compared with the usual care group. The results of the evaluation will be used to determine the within-trial cost-effectiveness (and utility) of the SHAReD intervention i.e. whether it offered value for money.

The results will be shown graphically on a cost-effectiveness plane.³² Thus, the cost-effectiveness plane will show the differences in healthcare costs and health effects/benefits between the SHAReD intervention and usual care groups in two dimensions, with the healthcare costs plotted against health effects/benefits. We will use the bootstrap method, which is a re-sampling method used to estimate basic statistics on a population through sampling the dataset with replacement, to create 10,000 random samples and then use these samples to establish a statistical distribution for the costs and health effects/benefits (means and standard deviations) in the intervention and control groups, as well as to generate confidence intervals for the applicable ICER.³³ Various sensitivity

analyses will be undertaken. We will also generate a cost-effectiveness acceptability curve to summarise the impact of uncertainty on the results of the evaluation, expressed as the main ICER in relation to possible values of the cost-effectiveness threshold.³⁴ Values for thresholds will be determined by considering what is meaningful for the healthcare provider.

Health related quality of life will be collected using the EuroQol five dimensions, 5 levels questionnaire (i.e. EQ5D5L), which is a reliable and validated utility-based and disease-generic quality of life measure used for medical decision-making in Australia and elsewhere. The cost-effectiveness study will use QALYs gained as one of the main health effects based on the EQ5D5L questionnaires administered at baseline, during, and at completion of the trial. Factors for changes in the quality of life (including the various domains, visual analogue score, overall score and QALYs) of study participants over time will also be explored using a range of econometric methods, such as difference in difference models, generalised linear mixed models (GLMMs) for repeated measures /panel data and other panel data methods.

The effects of the SHAReD intervention on employment and other activities undertaken by participants (and costed out) will be examined using summary statistics and logistic/probit models.

The economic evaluation will apply established principles and methods for undertaking cost-effectiveness (and cost-utility) analyses, consistent with the National Health and Medical Research Council's (NHMRC) economic evaluation guidelines.³⁵

